8.2.2.2. Exposure of this drug

Using the safety analysis set, exposure of this drug will be summarized with respect to the following aspects:

- Duration of treatment [1 day, 2 days, 3 days, 4 days, 5 days, 6 days, 7 days or more]: The number of days from the date of first dose to the date of last dose in this study, including non-dosing periods.
- Number of days of treatment [1 day, 2 days, 3 days, 4 days, 5 days, 6 days, 7 days or more]: The number of days this drug is actually administered in this study.
- Dose per administration (nirmatrelvir/ritonavir) [only 300 mg/100 mg, other than 300 mg/100 mg present (150 mg/100 mg present, other doses present)] [Breakdown of other]: Descriptions in parentheses indicate the breakdown of "other than 300 mg/100 mg present" and patients may overlap.

The duration of treatment is defined as the number of days from the date of first dose to the date of last dose in this study, including non-dosing periods. The number of days of treatment is defined as the number of days this drug is actually administered.

8.2.3. Safety analysis

Refer to Section 6.1 for the evaluation period for adverse reactions and adverse events. The listing will include all events reported in this study.

8.2.3.1. Adverse reactions

8.2.3.1.1. All adverse reactions

Adverse reactions will be summarized by SOC and PT in terms of number and proportion.

8.2.3.1.2. Serious adverse reactions

Serious adverse reactions will be summarized by SOC and PT in terms of number and proportion.

8.2.3.1.3. Details of adverse reactions

Adverse reactions will be summarized by SOC and PT in terms of number and proportion by each of the following factors:

- Seriousness [serious, non-serious]
- Known/unknown [known, unknown]
- Action taken [permanent discontinuation, temporary discontinuation or dose reduction]
- Outcome [fatal, not recovered, recovered with sequelae, improved, resolved/recovered, unknown]
- Outcome [fatal]

Multiple adverse reactions of the same PT occurring in the same patient will be handled as follows:

• Seriousness: If both serious and non-serious reactions of the same PT occurred in the same patient, the patient will be counted as one with serious reaction.

- Known/unknown: If both known and unknown reactions of the same PT occurred in the same patient, the patient will be counted as one with unknown reaction.
- Action taken: If multiple actions were taken for adverse reactions of the same PT, only one category of action will be adopted with "permanent discontinuation," "temporary discontinuation or dose reduction," and "dose increase or no change" being given priority in this order.
- Outcome: The outcome for the last event will be adopted.

8.2.3.1.4. Outcome of adverse reactions

For events with PTs of dysgeusia, taste disorder, diarrhoea, vomiting, nausea, decreased appetite, and rash, summary statistics of the time (days) from the start date of treatment with this drug to the onset date of the initial adverse reaction and the time (days) from the onset date of the initial adverse reaction to the date of resolution/recovery will be calculated in accordance with Section 8.1.1. The number of patients without resolution or recovery will be presented.

In addition, summary statistics will be tabulated for each of the above 7 events of PTs, other events, and all events according to the following definitions in accordance with Section 8.1.1.

- Time (days) from the start date of treatment with this drug to the onset date of the adverse reaction that occurred first among the initial events within each PT
- Time (days) from the onset date to the date of resolution/recovery of the adverse reaction with the longest time among the initial events within each PT: If the initial event did not resolve or recover in any PT, the patient will not be included in this tabulation and will be presented in the number of patients without resolution or recovery.

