#### 8.3.10. Adverse events

Occurrence of adverse events from the start date of administration of this drug to the end date of the observation period should be confirmed and the following information should be recorded.

Also, further investigation should be separately conducted, if deemed necessary by Sponsor for patients who experienced a serious adverse reaction, an unexpected adverse reaction or other adverse reactions not listed in the package insert.

- Presence/absence of adverse event
- Name of adverse event
- Date of occurrence
- Intervention
- Seriousness
- Outcome
- Causal relationship to this drug

If the adverse event is associated with abnormal laboratory values, i.e., clinical laboratory tests, the following information should also be recorded.

- Date of tests
- Name of laboratory test
- Site reference value
- Site unit
- Test results

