- Resolution of symptoms after worsening of severity during the observation period as of the end date of the observation period: For patients with worsening of severity during the observation period, the absence of symptoms on the end date of the observation period will be considered as resolution of symptoms and evaluated. It consists of the following categories. Even if the end date of the observation period and the date of the highest severity are the same, the patient will be included in the analysis.
 - Resolved, not resolved, unknown (resolution unknown, symptoms not recorded)
- Improvement in severity after worsening of severity during the observation period as of the end date of the observation period: For patients with worsening of severity during the observation period, improvement from the highest severity on the end date of the observation period will be evaluated. It consists of the following categories. Even if the end date of the observation period and the date of the highest severity are the same, the patient will be included in the analysis.
 - Improved, not improved, unknown (improvement unknown, severity not recorded)
- Death from any cause: Death reported by Day 28 after the end of treatment will be considered as an event and evaluated. Death should be confirmed with the outcome information of adverse events. Unknown if no adverse event is reported (Section 10.1 Table 1).
 The number of days from the start date of treatment to the onset date of event will be calculated. If an event including the case of unknown has not occurred, the patient will be censored at the date of the last observation or Day 28 after the end of treatment, whichever is earlier.

The following efficacy endpoint is defined in Efficacy Analysis Sets 2 and 3.

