8. STATISTICAL METHODS AND ANALYSES

8.1. Statistical Methods

8.1.1. Continuous variables

For continuous variables, summary statistics (n, mean, standard deviation, median, 1st quartile, 3rd quartile, maximum, and minimum) will be calculated.

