10.2. Appendix 2: Data Extraction Details

 Table 2.
 Definitions of Acceptable Windows for Timing

Timing	Endpoint	Definition [acceptable window]
At the start of treatment	Efficacy endpoints, viral load, body temperature, percutaneous arterial oxygen saturation	From 30 days prior to the date of first dose in this study (start date of treatment) to the start date of treatment
During the observation period	Safety endpoints, efficacy endpoints, viral load, body temperature, percutaneous arterial oxygen saturation, concomitant drug therapy, and non-drug therapy	Start date of treatment to Day 28 after the end of treatment
End date of the observation	Efficacy endpoints	Primary definition: Up to Day 28 after the end of treatment
period		Secondary definition 1: Up to 42 days after the end of treatment
		Secondary definition 2: Entire period

10.3. Appendix 3: Data Entries Related to Efficacy Endpoints and Their Handling, and Assessment of Endpoints

Table 3. Worsening of Severity and Highest Severity of Infection Caused by SARS-CoV-2

Symptoms	Severity at			Worsening of	of severity: H	ighest sev	erity			
at the start of	the start of treatment	Worsening	Vorsening of severity during the observation period							
treatment	with this	Absent		Present						
with this	drug	Highest seve	erity	ity						
drug		NA	Mild	Moderate I	Moderate II	Severe	Unknown	NA		
Absent	NA	Absent: NA	Present: Mild	Present: Moderate I	Present: Moderate II	Present: Severe	Present: Unknown	Unknown: NA		
Present	Mild		Case 1				Case 2			
	Moderate I									
	Moderate II									
	Severe	Severe at the start: NA	Case 3							
	Unknown	Absent: NA	Case 4							
Unknown	NA	Case 5								

NA: not applicable

Discrepancies between evaluations at the start of treatment with this drug and during the observation period are subject to re-investigation, but the reasons for being subject to re-investigation and handling of cases where there is no change as a result of re-investigation are shown below.

- Case 1: Assessed as "Unknown: NA" because the highest severity is lower than the severity at the start of treatment with this drug.

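### Time from onset to resolution of adverse reactions is summarized among resolved reactions only, so reported durations are too short whenever reactions outlast follow-up

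*SAP*

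**What the plan says.** SAP 8.2.3.1.4 (Outcome of adverse reactions) covers seven named PTs: dysgeusia, taste disorder, diarrhoea, vomiting, nausea, decreased appetite and rash. It asks for two times, start of treatment to first onset and first onset to resolution, and sends both to SAP 8.1.1, under which "summary statistics (n, mean, standard deviation, median, 1st quartile, 3rd quartile, maximum, and minimum) will be calculated". The number of patients without resolution is also shown.

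A second tabulation covers each of the seven PTs, other events, and all events. It takes each patient's longest duration among the initial events within each PT. "If the initial event did not resolve or recover in any PT", the SAP continues, "the patient will not be included in this tabulation and will be presented in the number of patients without resolution or recovery".

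Four other places bear on this:

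- SAP 8.2.3.1.3 tabulates adverse reactions by "Outcome [fatal, not recovered, recovered with sequelae, improved, resolved/recovered, unknown". For repeated reactions of the same PT its rule is "Outcome: The outcome for the last event will be adopted", whereas 8.2.3.1.4 works from the initial event.
- SAP 6.2 handles event-free patients differently for death from any cause: "the patient will be censored at the date of the last observation or Day 28 after the end of treatment, whichever is earlier".
- SAP Appendix 2, Table 2 sets the window for safety endpoints as "Start date of treatment to Day 28 after the end of treatment". Protocol 8.3.10 gives a similar period: "Occurrence of adverse events from the start date of administration of this drug to the end date of the observation period should be confirmed".
- Protocol 10.3 requires the investigator to follow causally related events until they resolve or settle at a level that the investigator and the sponsor accept.

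**The concern.** A reaction still present when observation stops has a duration that is known only to exceed the time observed. SAP 8.1.1 cannot use that information. The longest-duration tabulation excludes such patients expressly. The by-PT summaries exclude them by implication, since no duration can be computed without a resolution date. When the reason for non-resolution is that the reaction outlasted follow-up, the missing values are the longest ones, and every location statistic moves down.

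The pooled rows lose more. If the exclusion phrase means at least one unresolved PT, a single persistent reaction removes the whole patient, including the durations of that patient's resolved reactions.

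A reader will take this table as showing how long taste, gastrointestinal, appetite and skin reactions last. It will show how long the resolved ones lasted.

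**Working it through.** **Inputs.** The documents give no expected duration and no unresolved share, so there is no planned figure to reproduce. From the documents: a usual 5-day course, observation to 28 days after the end of treatment, and 3000 patients with a 7.8% reaction incidence (3000 × 0.078 = 234 patients with a reaction). Everything else below is an assumption, used only to show size.

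**1. One PT, fixed follow-up.** Let u be the share unresolved, with these being the longest durations, and Q(p) the quantile of all durations. The resolved-only quantile at p is then Q(p(1−u)). At u = 10% the reported quartiles are really the 22.5th, 45th and 67.5th percentiles.

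Exponential example at u = 10%:

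- Median ratio = −ln(1 − 0.5 × 0.9) / ln 2 = 0.598 / 0.693 = 0.86, so 14% short.
- Mean ratio = 1 − (−ln u) × u / (1−u) = 1 − 2.303 × 0.1 / 0.9 = 0.74, so 26% short.

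Range over exponential, Weibull (shape 0.7) and lognormal (sigma 1) durations (the time scale cancels):

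| Unresolved | Median short by | Mean short by |
|---|---|---|
| 2% | 2–4% | 8–14% |
| 5% | 6–10% | 16–25% |
| 10% | 12–19% | 26–39% |
| 20% | 22–35% | 40–56% |

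**2. Link to the observation window.** Five days of treatment plus 28 days ends on Day 33; onset on Day 3 leaves 30 days. If resolution dates were held to that window, the unresolved share for exponential durations with median m days would be 2^(−30/m): 0.1%, 1.6%, 5.1%, 12.5% and 22.6% for m = 3, 5, 7, 10 and 14. In days:

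| True median | Resolved-only median | Upper quartile, resolved-only (true) | Mean, resolved-only (true) |
|---|---|---|---|
| 3 | 3.0 | 6.0 (6.0) | 4.3 (4.3) |
| 7 | 6.5 | 12.6 (14.0) | 8.5 (10.1) |
| 14 | 9.9 | 17.5 (28.0) | 11.4 (20.2) |

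**3. Pooled rows.** Take 10% unresolved in each PT and exclude the patient if at least one is unresolved. If PTs are independent, 1 − 0.9² = 19% of two-PT patients and 1 − 0.9³ = 27% of three-PT patients are lost. With Gaussian-copula correlation 0.5 the losses are 17% and 22%. In 1,000,000 simulated patients with exponential durations, the median of the longest duration is 18% short with two PTs and 21% short with three.

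**4. When the direction changes.** If 10% have an unknown outcome unrelated to duration, the resolved-only median is unbiased (ratio 1.00). If those 10% come from the shorter half, as when recovered patients do not return, it is too long (1.13–1.22).

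**5. What Kaplan-Meier recovers.** With 234 reactions, onset on Days 1–6, follow-up to Day 33 and whole-day durations, the Kaplan-Meier medians were 7.5, 14.4 and 21.3 days against true values of 7.5, 14.5 and 21.4. The resolved-only medians were 7.0, 10.3 and 11.8.

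The correction is partial when censoring depends on persistence. In sets of 100 exponential durations, with the longest 10% or 20% censored between onset and the true median, Kaplan-Meier gives 0.93 or 0.87 of the true median, against 0.86–0.87 or 0.74 for resolved-only. If the longest are censored at onset, the two methods coincide.

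Kaplan-Meier overstates if 10% are coded unknown although they resolved unseen: by a factor of 1.05–1.12 when this is unrelated to duration, and about 1.17 (exponential) when they come from the shorter half.

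**The case against.** **The plan discloses the exclusions.** The unresolved count is printed, n is printed, and SAP 8.2.3.1.3 tabulates outcomes by PT. A resolved-only summary beside that count is a legitimate conditional description, and the SAP never says that it estimates duration among all reactions. This stands as far as transparency goes. It does not repair the statistics: nobody can recover a median or quartile for all reactions from resolved-only quartiles and a count. The outcome table also takes the last event of a PT, not the initial one, so the two tables need not agree.

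**Follow-up of related events may run past Day 28.** Protocol 10.3 applies to exactly these reactions, and no passage states that resolution dates are cut at the window. This also stands: the Day 33 shares above are conditional and may be too high. But follow-up may end at stabilization, which is not resolution, and SAP 8.2.3.1.4 does not say whether later dates are used.

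**The size is assumed, and Kaplan-Meier has its own bias.** Both are true. For unknown outcomes the direction depends on why the status is unknown, which is why a sensitivity analysis belongs in the fix.

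**Safety and efficacy are handled consistently within themselves.** The censoring rule for death is an efficacy rule, so the contrast is not a contradiction. It shows only that the method is already in the SAP.

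**The study is exploratory and the table secondary.** Agreed, and this limits the weight of the point.

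**Conclusion.** The concern holds. As written, SAP 8.2.3.1.4 gives durations for resolved reactions only, and these are too short for all patients with the reaction whenever reactions outlast follow-up or status is lost on persistent ones. Confidence is high in the mechanism and its direction in that situation. The size cannot be taken from the documents: it is negligible if almost everything resolves within days, roughly 6–10% on the median at 5% unresolved, and 22–35% at 20% unresolved. These figures rest on the assumed distributions and on the unresolved reactions being the longest. The pooled figures also rest on reading the exclusion as at least one unresolved PT. Only this descriptive safety table is affected. It should be corrected because the correction is cheap, but nothing else in the plan depends on it.

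**What to change.** In SAP 8.2.3.1.4, for onset-to-resolution time only, replace the reference to 8.1.1 by the Kaplan-Meier method of 8.1.4, and specify:

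- **Origin and event:** reaction onset; resolution or recovery.
- **Censoring:** unresolved reactions at the last date their status is known. Show fatal outcomes separately.
- **Outcome classes:** whether improved and recovered with sequelae count as resolved, and whether resolution dates after Day 28 are used.
- **Unknown outcomes:** censored in the main analysis, left out in a sensitivity analysis.
- **Pooled rows:** a patient is resolved only when all initial reactions have resolved.
- **Alongside:** the resolved-only statistics, labelled as such, and the percentage unresolved.
- **If the upper quartile is not reached:** the proportion resolved at the 8.1.4 day points (3, 5, 7, 14, 21, 28), counted from onset. In simulated sets of 100 this happened in roughly 10%, 45% and 84% of sets at 20%, 25% and 30% unresolved.

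The cost is low: SAP wording, a new time origin, an outcome classification and a censoring date. SAP Section 7 already names onset and resolution dates. A last-status date may have to be derived, because Protocol 8.3.10 lists date of occurrence and outcome but no such item, and SAP version 5 already records the study as completed. The minimum acceptable change is to label the table as resolved reactions only and print the unresolved percentage beside it. That makes the table honest but leaves the durations uncorrected.

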8.2.3.1.5. Safety specifications

For the following safety specifications, patients who experienced relevant events will be summarized in terms of number and proportion:

- Toxic epidermal necrolysis/oculomucocutaneous syndrome
- Hepatic impairment
- Hyperglycemia/diabetes mellitus
- Bleeding tendency

In addition, patients who experienced each safety specification will be summarized by action taken and outcome for each SOC and PT.

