		9.4. Ethical conduct of the study		
		10. MANAGEMENT AND REPORTING OF ADVERSE EVENTS/ADVERS E REACTIONS	Changes in Japanese translation, etc., and maintenance of descriptions	Due to changes in association with a revision of the in-house form
		12. NAME, AND ADDRESS OF CONTRACTOR AS WELL AS SCOPE OF WORK CONTRACTED	Maintaining address information	Administrative changes
		16.2. Contact information for inquiries about the EDC system (In the case of study using EDC)	Changes in contact information for inquiries	Due to changes in the information concerning contact information
Amended 1	28 June 2022	7.1. Safety specifications	Added anaphylaxis to important identified risks	Due to the revision of safety specification in the Risk Management Plan
		8.7. Data analysis	Definition of analysis set     Change before:  R CONFIDENTIAL	The effectiveness analysis set was not a subset of safety populations,

			· Effectiveness Analysis Set 1: A population of patients in the SAS excluding patients for whom effectiveness evaluation is not reported at all or whose disease is not subject to the study After change: · Effectiveness Analysis Set 1: A population of patients in which effectiveness can be evaluated among patients in which this drug was administered	but effectiveness evaluable among all patients with administration
		10. MANAGEMENT AND REPORTING OF ADVERSE EVENTS/ADVERS E REACTIONS	Changes in Japanese translation, etc., and maintenance of descriptions	Due to changes in association with a revision of the in-house form
		12. ORGANIZATION AL SYSTEM FOR STUDY IMPLEMENTATIO N	Item Removal (Subsequent section numbers moved up)	Administrative changes associated with the Notification "Formulation and Publication of Risk Management Plans" dated 18 March 2022
FINAL	08 February 2022	N/A	N/A	N/A

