# 7.1. Safety specifications

Important Identified Risks: Toxic epidermal necrolysis/oculomucocutaneous syndrome, hepatic function disorder and anaphylaxis

Important Potential Risks: Hyperglycemia/diabetes mellitus and bleeding tendencies

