1. REVISION HISTORY

Version/	Summary of Changes/Comments
Date/	
Author(s)/	
Status of Study	
1	First edition
26-Apr-2022	
PPD	
Ongoing	
2	Section 2.1: Changed to refer to other documents for safety specifications.
1-Dec-2022	Section 5.2: Description adjustment
PPD	• Sections 5.4, 8.2.2.1, and 8.2.3.3: Added specific definitions of subgroups.
Ongoing	Section 6.3: Added handling of multiple measurements on the same day.
	Section 7: Deleted laboratory test dates from dates used to supplement dates.
	• Section 8.2.2.1: Added age and body weight to patient characteristics, and deleted the experience of treatment with Paxlovid.
	o Section 8.2 3.1.5: Included the patients excluded from the safety analysis set in the
	tabulation of the occurrence of adverse reactions.
3	Section 5.2: Changed terms used in Exclusion Criterion 1 for efficacy analysis set
13-Jun-2023	in association with the revision of the inclusion/exclusion criteria for analysis sets
PPD	and guidance for data handling to Version 3.
Ongoing	Section 5.3: Added analysis sets concerning informed consent.
	Section 5.4: Added and deleted subgroups and provided reference levels
	 Section 6.2: Added a sensitivity analysis of hospitalization for the treatment of infection caused by SARS-CoV-2 or death from any cause.
	Section 8.1 3: Added graphical representation of risk ratio.
	Section 8.1.4: Adjusted the description about the number of days for time data,
	and added the specification for subgroup analyses.
	Section 8.2: Added analysis sets concerning informed consent.
	Section 8.2.2.1: Added patient characteristics and added/changed categories.
	• Section 8.2. 3.1.4: Added an analysis on the outcome of adverse reactions.
	• Section 8.2.3.2: Deleted the tabulation of all adverse events.
	Section 8.2.3.2.1: Changed the method of tabulation of serious and non-serious
	adverse events.
	 Section 8.2.3.3: Specified adverse reactions to be analyzed in subgroup analyses and added estimation of risk ratio.
	• Section 8.2.4.6: Added the tabulation of patient characteristics in patients with events.
	Section 8.2.4.7: Added risk ratio and hazard ratio estimation in subgroup analyses.
	Section 9: Added listings.
	Section 10.5: Added examples of tables and figures for subgroup analyses.

Version/	Summary of Changes/Comments
Date/	
Author(s)/	
Status of Study	
4	Sections 5.4 and 8.2.4.6: Changed subgroup categories.
06-Jul-2023	 Section 8.2.2.1: Added patient characteristics and changed categories.

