2.1. Study Objectives

This study will be conducted in patients treated with this drug to understand the safety and efficacy of this drug under actual use conditions after marketing. For safety specifications, refer to the latest protocol or risk management plan.

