6. ENDPOINTS AND COVARIATES

6.1. Safety Endpoints

The safety evaluation period is defined as the observation period in Section 2.2. The number of days from the start date of treatment to the onset date of event will be calculated as [event onset date – start date of treatment with this drug + 1].

- Adverse reactions: Adverse events for which the causal relationship was considered as related by the treating physician
- Adverse events: All-causality adverse events
- Serious adverse events or serious adverse reactions: Adverse events or adverse reactions considered by the treating physician to be serious
- Events to be handled as safety specifications are specified separately.

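### The SAP's safety-specification summary lists four of the protocol's five specifications and leaves out anaphylaxis, an important identified risk

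*SAP*

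**What the plan says.** Protocol 7.1 sets out the safety specifications in two tiers. The important identified risks are "Toxic epidermal necrolysis/oculomucocutaneous syndrome, hepatic function disorder and anaphylaxis". The important potential risks are hyperglycemia/diabetes mellitus and bleeding tendencies.

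SAP 8.2.3.1.5 gives the analysis: "For the following safety specifications, patients who experienced relevant events will be summarized in terms of number and proportion". Its list names toxic epidermal necrolysis/oculomucocutaneous syndrome, hepatic impairment, hyperglycemia/diabetes mellitus and bleeding tendency. The section then asks for action taken and outcome, by SOC and PT, for the patients with each specification.

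Two other SAP passages touch the subject. Section 2.1 says "For safety specifications, refer to the latest protocol or risk management plan". Section 6.1 says "Events to be handled as safety specifications are specified separately".

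The general adverse reaction tables are ordered elsewhere. SAP 8.2.3.1.1 says "Adverse reactions will be summarized by SOC and PT in terms of number and proportion". SAP 8.2.3.1.3 repeats this by seriousness, known/unknown status, action taken and outcome.

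**The concern.** The SAP's pointer and its own list disagree. Section 2.1 sends the reader to the current protocol, which has five specifications. Section 8.2.3.1.5, the only place that orders a summary by specification, lists four. The one left out is an important identified risk, while both potential risks are listed.

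Protocol Section 13 commits the sponsor to reviewing risk minimization for the current safety specifications at each milestone, and Section 14 ties those milestones to reporting to the PMDA. A table by specification is the natural input to that review. If the SAP is followed as written, anaphylaxis will not be in it. A reader could not tell whether there were no cases or whether the question was not tabulated.

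**Working it through.** The check is a comparison of two lists in the current documents (protocol Version 3, SAP Version 5). The amendment and revision logs are used only for dates.

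**Step 1: match the lists.**

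| Protocol 7.1 | Tier | SAP 8.2.3.1.5 |
|---|---|---|
| Toxic epidermal necrolysis/oculomucocutaneous syndrome | identified | listed |
| Hepatic function disorder | identified | listed (as hepatic impairment) |
| Anaphylaxis | identified | **not listed** |
| Hyperglycemia/diabetes mellitus | potential | listed |
| Bleeding tendencies | potential | listed |

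Protocol: 3 identified + 2 potential = 5. SAP: 2 identified + 2 potential = 4. Missing: 5 − 4 = 1. The SAP lists nothing that the protocol does not. The two hepatic terms are taken to be the same specification in different words. The word anaphylaxis does not occur in the SAP text supplied.

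**Step 2: can the order of revisions explain the gap?** SAP Version 1 is dated 26 April 2022. Protocol Amendment 1, dated 28 June 2022, records "Added anaphylaxis to important identified risks" (protocol Section 4). Four SAP versions followed: Version 2 (1 December 2022), Version 3 (13 June 2023), Version 4 (6 July 2023) and Version 5 (8 September 2023). From 28 June 2022 to 8 September 2023 is 365 + 72 = 437 days. The Version 2 entry for Section 2.1 reads "Changed to refer to other documents for safety specifications". No entry in the revision history adds anaphylaxis to the list, and none gives a reason for leaving it out. The pattern fits a list written before the amendment and never updated.

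**Step 3: do the pointers supply the table?** Section 2.1 sits under the study objectives and says where the specifications are named. Section 6.1 says where the qualifying events are defined. Neither asks for an output. Section 8.2.3.1.5 does, for a closed list with no cross-reference. SAP Section 3 says the final analysis covers the items defined in the SAP, so a programmer working from it would build four groupings.

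**Step 4: what do the general tables already give?**

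| Output for anaphylaxis | Available without 8.2.3.1.5? |
|---|---|
| Related reactions by PT, number and proportion | yes, 8.2.3.1.1 |
| Serious reactions by PT | yes, 8.2.3.1.2 |
| Action taken and outcome by SOC and PT | yes, 8.2.3.1.3 |
| Patient listings of adverse reactions and serious events | yes, Section 9 |
| Number and proportion of patients with any event in the specification | no |
| Explicit zero if there is no case | no |

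If the separate event specification assigns several PTs to anaphylaxis, adding their rows counts a patient with two of those PTs twice, so the rows do not give the grouped patient count. A PT table also has no row for a term that nobody reported.

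**Step 5: are other planned figures affected?** They are not. As context, the sample size statement reproduces: the smallest n with 1 − 0.999^n ≥ 0.95 is ln 0.05 / ln 0.999, rounded up to 2995, and 1 − 0.999^3000 = 0.9503. Adding anaphylaxis changes neither this figure nor any denominator.

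**The case against.** The strongest reply is that the SAP already contains the governing rule. Section 2.1 defers to the latest protocol, the latest protocol includes anaphylaxis, and so the list in 8.2.3.1.5 is merely out of date. The section's second sentence refers to each safety specification without limiting itself to those listed. The separate event specification and the risk management plan are not available here and may already cover anaphylaxis, as may the re-examination and periodic safety report forms required by SAP Section 9. The protocol's own analysis section (8.7) asks only for the number and proportion of patients with adverse reactions, with no table per specification. Finally, related cases are visible in the general tables and listings, the study is descriptive, and the number of days or versions since the amendment says nothing about the effect on results.

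Much of this stands. The documents prove an inconsistency; they do not prove that the final output will lack the row. The action and outcome information is largely preserved at SOC and PT level by 8.2.3.1.3. The dates show how the gap arose and that it persisted, not how large it is. This is an alignment slip: nothing suggests that anyone decided to exclude anaphylaxis.

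It does not remove the point. A pointer in the objectives does not override an explicit list in the section that orders the table, and event terms held in another document produce no row unless the SAP asks for one. Inferring zero from an absent PT also requires the reader to know which terms were searched.

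**Conclusion.** The point holds. SAP 8.2.3.1.5 covers 4 of the 5 current safety specifications: 2 of 3 important identified risks and 2 of 2 important potential risks. As written, anaphylaxis gets no grouped number and proportion of patients, no explicit zero, and no action and outcome summary presented under its own specification. The underlying reactions are not lost, and no endpoint, denominator, sample size or case-level record changes.

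Confidence in the mismatch is high. The conclusion about the output assumes that the programming follows the list in 8.2.3.1.5, and that hepatic impairment there means the protocol's hepatic function disorder. The gap is small, but it concerns an identified risk in a study whose results feed the risk management review, so it should be corrected.

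**What to change.** Add anaphylaxis to the list in SAP 8.2.3.1.5, and confirm that its event terms are in the separate specification cited in SAP 6.1. Alternatively, replace the fixed list with an express reference to the specifications in current protocol 7.1 or the risk management plan, so that the table follows any later change. With either change, report a zero count where no case occurs.

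The cost is one line in the SAP and one more event grouping in an existing table program, with no new data collection. The planned dates for database release (November 2024) and the final study report (October 2025) both fall after SAP Version 5, so the planned schedule leaves room for the change.
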